#### 5.4.2 Secondary Efficacy Analyses

The FAS will be used to summarize seizure freedom data and conversion data of perampanel as a 1st adjunctive therapy converted to perampanel monotherapy. The number and percentage of subjects who achieved seizure-free status or who converted to perampanel monotherapy will be summarized. 95% CIs may also be calculated if allowed by the data.

The seizure-free status at 3-month in Maintenance Period, at 6-month in Maintenance Period, and during the entire Maintenance Period will only be counted for subjects who complete the respective period. A subject who dropped out early relative to the respective period would be counted as 'No' for seizure-free status in that period.

A subject is considered converted to perampanel monotherapy during Maintenance Period if the subject had a scheduled visit in Maintenance Period and was not taking any concomitant AED at any time during the scheduled visit. A subject who dropped out early before the conversion would be counted as 'No' for conversion status.

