#### Maintenance Period

Subjects will continue to receive the perampanel dose level that was administered at the end of the Titration Period, when they enter the 39-week Maintenance Period. Subjects will come to the study site for Visit 4 (Week 13), Visit 5 (Week 26), Visit 6 (Week 39), Visit 7 (Week 52), and at the Follow-Up Visit (Visit 8). All subjects who discontinue the study are to complete the study's early discontinuation procedures indicated in the Schedule of Procedures/Assessments. (revised per Amendment 01)

According to the investigator's clinical judgment, subjects who experience AEs may have their perampanel dose reduced. Conversely, if seizures are not adequately controlled, subjects may have their dose increased up to a maximum of perampanel 12 mg. During the Maintenance Period, subjects whose perampanel dose has been reduced may have the dose increased again, at the discretion of the investigator, as soon as tolerability improves. Subjects who cannot tolerate a dose of 4 mg will discontinue perampanel treatment and be withdrawn from the study. Adjustment of the concomitant AED dose level during the Maintenance Period is permitted. Subjects who receive perampanel as a 1st adjunctive therapy may also be converted to perampanel monotherapy at the discretion of the investigator. All adjustments to concomitant AED dose levels must be reported in the eCRF.

The overall study design is depicted in [Figure 1](#).

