#### 9.4.7 Prior and Concomitant Drug/Therapy

- Concomitant AED for subjects who receive perampanel as a 1st adjunctive therapy

- Only 1 AED can be used.
- A concomitant AED must be used at the stable dose and administered between 8 weeks before Visit 2 (Week 0) and the end of the Titration Period. The dose and administration of the AED may be modified during the Maintenance Period based on the investigator's judgment.
- Concomitant medication  
The following concomitant drugs are prohibited throughout the study period (up to the Follow-Up Period or early discontinuation visit): (revised per Amendment 01)
  - CYP3A4-inducing drugs and food below as follows (from 30 days before Visit 1): Rifampicin, troglitazone, barbiturates except for use as AED, modafinil, efavirenz, nevirapine, glucocorticoid except for topical use, pioglitazone, rifabutin, and food containing St. John's Wort (*Hypericum perforatum*). (revised per Amendment 01)
  - Antipsychotics
  - Other investigational drugs. (revised per Amendment 01).
  - CBD products (revised per Amendment 01)Restricted concomitant drug:
  - Any changes in the dosing regimen of antidepressant or antianxiety drugs during the study must be recorded.
  - Barbiturates (except for seizure control indication and premedication for EEG) and benzodiazepines (except for seizure control indication) within 8 weeks prior to Visit 2 (Week 0)
- Concomitant therapy (revised per Amendment 01)  
Prohibited concomitant therapy  
The following therapies must not be implemented during the study:
  - Investigational deviceRestricted concomitant therapy:
  - Vagus nerve stimulation is allowed, but stimulator parameters cannot be changed for 8 weeks before Visit 2 (Week 0) or thereafter during the study.
  - A ketogenic diet will be allowed as long as the subject has been on this diet for 8 weeks prior to Visit 2 (Week 0). Additionally, a ketogenic diet cannot be newly added or discontinued during the study.Clarification of previous AED medication:
  - Subjects may switch monotherapies provided the time to complete the conversion is less than 30 days.
  - Subjects on short-term monotherapy (<2 weeks) may be eligible for the study provided they stop the initial therapy at the time of perampanel dosing.

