### 5.1.2 Secondary Endpoints

- Proportion of subjects who achieve seizure free status for POS, SGS, and PGTCs during the Maintenance Period.
- Proportion of subjects who achieve 3-month seizure-free status for POS, SGS, and PGTCs.
- Proportion of subjects who achieve 6-month seizure-free status for POS, SGS, and PGTCs.
- Proportion of subjects who receive perampanel as a 1st adjunctive therapy who are able to convert to perampanel monotherapy
- Safety and tolerability of perampanel administered as monotherapy or 1st adjunctive therapy in adolescents and adults
- Maximum and last dose during the titration period and the maintenance period

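### Conversion to monotherapy is scored from AED status at a scheduled Maintenance visit with no seizure criterion, so the rate measures withdrawal of the other AED rather than successful conversion

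*SAP*

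**What the plan says.** The secondary endpoint in SAP 5.1.2 is "Proportion of subjects who receive perampanel as a 1st adjunctive therapy who are able to convert to perampanel monotherapy". The secondary objective (Protocol 8.2, SAP 3.1.2) uses the same idea of ability. Neither document defines it.

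The operational rule is in SAP 5.4.2: a subject is converted if "the subject had a scheduled visit in Maintenance Period and was not taking any concomitant AED at any time during the scheduled visit". On missing outcomes it adds: "A subject who dropped out early before the conversion would be counted as 'No' for conversion status". It sets no seizure condition and no minimum time off the AED, and nothing reverses a 'Yes' if an AED is restarted or perampanel is stopped later.

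Protocol 9.1.3 leaves the step to the investigator: first-adjunctive subjects "may also be converted to perampanel monotherapy at the discretion of the investigator". Protocol 9.4.7 says the dose and administration of the concomitant AED "may be modified during the Maintenance Period based on the investigator's judgment". Protocol 9.1.2 does not permit AED dose adjustment during Titration, so a compliant stop falls in Maintenance.

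Seizure endpoints are summarised by seizure type, overall, and by sex and age group (SAP 5, 5.3.4, 5.4.3). Conversion status is not among the subgroups.

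**The concern.** The endpoint's name and its rule measure different things. The name claims that subjects could manage on perampanel alone. The rule records that the other AED was absent at a scheduled visit. A subject who has more seizures after the stop, but attends one visit AED-free, scores the same as one who does well.

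SAP 5.4.2 is stricter about seizure freedom in the same section: only subjects who complete the relevant period can count as seizure-free. Conversion has no comparable safeguard once it has been scored.

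Protocol 7.2 names information on withdrawing previous AEDs in combination with perampanel as useful and connects such data to product labelling. The conversion proportion is the trial's most direct output on that question. A reader would naturally take a high figure as evidence of adequate control on perampanel alone, and the planned summaries would not let that reader check it.

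**Working it through.** **The plan's own figure.** There is none to reproduce. The documents give no expected conversion rate, target or precision. The only planning number is an enrolment of approximately 125, with no hypothesis to be tested (Protocol 9.7.2).

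**Step 1: the rule's inputs.** Converted = (a scheduled Maintenance visit took place) and (no concomitant AED at that visit). I read the wording as satisfied by any one such visit. Dropout before conversion gives 'No'. Seizure counts do not appear, although Protocol 9.5.1.2 has diaries reviewed at Visits 2, 4, 5, 6 and 7.

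**Step 2: indirect routes for seizures.** There are three.
- The investigator may not stop the AED in a poorly controlled subject (Protocol 9.1.3).
- The AED may be restarted before the next scheduled visit (Protocol 9.4.7).
- The subject may leave before that visit for lack of efficacy or inadequate therapeutic effect (Protocol 9.3.3.2, 9.5.5).

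Each works only if it prevents the stop or acts before an AED-free scheduled visit. On-site visits after Week 13 are 13 weeks apart (Weeks 26, 39, 52).

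**Step 3: an accounting illustration.** All values are assumptions.
- a = share of first-adjunctive subjects whose other AED is stopped
- p = share of those who worsen
- r = share of the worsened who restart an AED or leave before their next scheduled visit

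Rate under the SAP rule = a(1 − p·r). Rate without worsening = a(1 − p). The difference is a·p·(1 − r).

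With a = 0.50 and p = 0.30, the rate without worsening is 0.50 × 0.70 = 35%. For comparison, p = 0.70 stands for perampanel doing nothing, where the rate without worsening is 0.50 × 0.30 = 15%.

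| r | SAP rule, p = 0.30 | Excess over 35% | SAP rule, p = 0.70 | Gap between the SAP-rule columns |
|---|---|---|---|---|
| 0 | 50% | 15 points | 50% | 0 |
| 0.25 | 46.3% | 11.3 | 41.2% | 5 |
| 0.5 | 42.5% | 7.5 | 32.5% | 10 |
| 0.75 | 38.8% | 3.8 | 23.8% | 15 |
| 1 | 35% | 0 | 15% | 20 |

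If investigators also stop the AED less often when perampanel does nothing (a = 0.30 with p = 0.70), the SAP rule gives 50% against 30% at r = 0, and 42.5% against 19.5% at r = 0.5.

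**Step 4: would seizure freedom to the end of Maintenance be a better criterion?** Assume Poisson seizures at rate λ per 28 days over T weeks, so P(seizure-free) = exp(−λT/4). At an assumed λ = 0.25:
- AED stopped at Week 13, T = 39: exp(−2.4375) = 9%
- AED stopped at Week 48, T = 4: exp(−0.25) = 78%

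The same underlying control would give very different success rates, depending on when the AED was stopped.

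**The case against.** The strongest defence is that conversion and seizure control are separate secondary objectives. Protocol 7.2 asks for real-world information on withdrawing other AEDs, and a descriptive withdrawal proportion supplies it. To require a seizure outcome is to choose a meaning for 'able' that neither document states. Seizure results are reported alongside, and a cross-tabulation may exist in the table shells, which SAP 11 keeps in a separate document. The endpoint is secondary and descriptive, in a trial without a control arm whose enrolment ended early (SAP 7).

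Much of this stands. It supports keeping the current rate and limits how serious the point is. It does not support a label that claims ability, and the shells cannot be credited with an analysis that the SAP does not plan.

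A reader might infer three stronger things, none of which holds:
- **That the rate would be the same if perampanel did nothing.** In the illustration this needs r = 0 and a decision to stop the AED that ignores seizure control. At equal a, every r above 0 that was tried separates the two cases, by 5 to 20 points.
- **That only the AED record is used.** Visit attendance and the dropout rule also enter.
- **That no planned analysis covers the time after the stop.** The whole-Maintenance seizure summaries do cover it. They mix it with time before the stop and do not separate converters.

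**Conclusion.** The point holds in this form: conversion is scored with no seizure criterion, so unsuccessful conversions can be counted as successes, and the planned summaries cannot identify them. The rate is a measure of AED withdrawal.

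The size of the overstatement cannot be found from the documents. With 50% stopped and 30% of those worsening, both assumed, it runs from 0 to 15 percentage points, depending on how many worsened subjects restart or leave before being seen. With no control arm, the rate cannot be attributed to perampanel under any definition.

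The issue deserves correction because it concerns a stated secondary objective and the repair is cheap. It does not touch the primary endpoint.

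**What to change.** In SAP 5.4.2:

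1. Keep the present rate and label it 'concomitant AED withdrawn during Maintenance'.
2. Add a supportive rate over the same first-adjunctive denominator: n (%) converted who stayed on perampanel, did not restart an AED, and had no increase in seizure frequency per 28 days after the AED stop. Compare with on-treatment frequency before the stop, taking Titration plus Maintenance together, so that the comparison exists for stops early in Maintenance.
3. List, for each converter, the baseline, pre-stop and post-stop seizure frequency and the length of follow-up after the stop.
4. Do not tie ability to convert to seizure freedom until the end of Maintenance, because that depends on the date of the stop.
5. State which visits count as scheduled Maintenance visits. Protocol Table 4 places Week 13 under Maintenance, while the SAP 8.2.2 mapping table places it under Titration. The effect is probably small, because a stable AED dose is required to the end of Titration.

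The inputs should already be available: AED adjustments go into the eCRF (Protocol 9.1.3), AED treatment is recorded throughout (9.5.1.1.5), and diaries and perampanel dose are collected (9.5.1.2, Table 4).

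The cost is SAP text, one table and one listing. Converters will be few, follow-up after the stop will be unequal, and the supportive rate can be no higher than the current one. For a subject with no seizures before the stop, 'no increase' is the same as seizure freedom, so some dependence on follow-up time remains. The listing shows that length for each subject.

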#### 5.4.3 Exploratory Efficacy Analyses

Analyses of exploratory efficacy endpoints will be performed in the subset of the FAS with sufficient baseline seizure frequency i.e. at least 1 seizure during the baseline. All summaries will be produced by seizure type (POS, SGS, and PGTCS).

For percent change in seizure frequency endpoints at each treatment Period [pre-treatment, treatment, (titration plus maintenance), maintenance and maintenance-LOCF], and for each seizure type:

- Mean, standard deviation, median, minimum, and maximum will be provided.

For responder rate endpoints at each time point (3, 6, 9, and 12 months in maintenance period, maintenance and maintenance-LOCF), and for each seizure type:

- Number and percentage of responders will be provided

95% confidence intervals for the percentage change and responder rate may also be calculated if allowed by the data.

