Study Design This is a multi-center, open-label, Phase 4 study. Subjects who meet all of the inclusion and none of

the exclusion criteria will receive perampanel. Baseline seizure counts (frequency) data will be collected by subjects or guardian/legally authorized representative, retrospectively (for history prior to screening) and prospectively as needed (during baseline). The study consists of 4 periods: a Screening Period (to start no earlier than 6 weeks before the 1st dose of study drug), a Titration Period (up to 13 weeks), a Maintenance Period (39 weeks), and a Follow-Up Period (4 weeks). (revised per Amendment 01)

Study subjects will include the following:

- Subjects who have been diagnosed with POS or PGTCS but have not previously received treatment with an antiepileptic drug (AED) or are currently receiving monotherapy treatment (no history of AED polytherapy) and wish to switch to another monotherapy treatment; or
- Subjects who are currently receiving treatment with a single AED administered at a stable dose for at least 8 weeks before Visit 2 (Week 0) and need additional AED treatment; subjects should not have previously received adjunctive AED therapy.

Screening Period

During the Screening Period, informed consent/pediatric assent will be obtained and screening assessments will be conducted. The Screening Visit (Visit 1) will take place no earlier than 6 weeks before the 1st dose of study drug. Seizure data from up to 12 weeks preceding the 1st dose should be collected by the investigator retrospectively and prospectively. Subjects will be eligible for study enrollment after they have experienced either the 2 required unprovoked (or reflex) seizures or the 1 unprovoked (or reflex) seizure with EEG evidence of seizures, and they will not need to complete the full 12-week diary to enter the Titration Period. (revised per Amendment 01)

Titration Period

The Titration Period will begin with Visit 2, which may overlap with the Screening Visit (Visit 1), and will last for up to 13 weeks. (revised per Amendment 01) Subjects will receive perampanel tablets once daily (QD) before bedtime. The initial dose of perampanel 2 mg/day may be up-titrated in increments of 2 mg according to the investigator’s judgment, based on individual clinical response and tolerability, as shown in the following dosing schedule:

Category	Week a	Perampanel Dose (mg/day)
Required	1	2
	2	2
	3	4
	4	4
		Telephone Visit

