#### 9.1.1 Screening Period (Week -6 ~ Week 0)

The Screening Visit (Visit 1) will take place no earlier than 6 weeks before the 1st dose of study drug. Seizure data from up to 12 weeks preceding 1st dose will be collected by the investigator, including retrospective data collection as needed. Subjects will be eligible for study enrollment after they have experienced either the 2 required unprovoked (or reflex) seizures or the 1 unprovoked (or reflex) seizure with EEG evidence of seizures, and they will not need to complete the full 12 week diary to enter the Titration Period. (revised per Amendment 01) Subjects without the required seizure data will fail screening, but may be rescreened 1 time. During the Screening Period, informed consent will be obtained and screening assessments will be conducted.

Before or at the Screening Visit (Visit 1), informed consent will be obtained after the study has been fully explained to each subject and before any baseline procedures or assessments are conducted. Procedures to be followed when obtaining informed consent are detailed in [Section 5.3](#).

Investigators will confirm the inclusion/exclusion criteria and will conduct the planned evaluations. Subjects should be no younger than 4 years of age and able to swallow perampanel tablets. They must have been diagnosed with epilepsy, consisting of POS with or without SGS or PGTCs. (revised per Amendment 01) Additionally, they must need monotherapy or they must need 1st adjunctive therapy with perampanel after failure to control seizures on monotherapy with another AED at the optimal dose and duration for that AED.

Screening results must be recorded on the appropriate electronic Case Report Form (eCRF) to indicate whether or not the subject is eligible to participate in the study and to provide reasons for screen failure if applicable. In addition, medical history, prior concomitant medications and prior concomitant AED of subjects will be obtained. Subjects who complete Visit 2 (Week 0) and meet all of the inclusion/exclusion criteria ([Section 9.3.1](#) and [Section 9.3.2](#)) will be enrolled and will begin the Titration Period.

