### 9.1.2 Titration Period

The Titration Period will begin with Visit 2, which may overlap with the Screening Visit (Visit 1), and will last for up to 13 weeks. (revised per Amendment 01) Subjects will receive perampanel tablets once daily (QD) before bedtime. The initial dose of perampanel 2 mg/day may be up-titrated in increments of 2 mg according to the investigator’s judgment, based on individual clinical response and tolerability, as shown in the following dosing schedule (Table 1):

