### 9.3.1 Inclusion Criteria

Subjects must meet all of the following criteria to be included in this study:

1. Subjects will be male or female and no younger than 4 years of age and be able to swallow perampanel tablets. (revised per Amendment 01)
2. Subjects must have a diagnosis of epilepsy with POS with or without SGS, or with PGTCS. Either of the following must have occurred to support an epilepsy diagnosis: (revised per Amendment 01)
  - a. At least 2 unprovoked (or reflex) seizures occurring greater than 24 hours apart

- b. 1 unprovoked (or reflex) seizure with EEG evidence of seizures
3. Subjects who receive perampanel as a 1st adjunctive therapy must currently have been treated with stable doses of monotherapy with an AED for 8 weeks prior to Visit 2 (Week 0), have not previously received adjunctive AED treatment, and must, in the investigator's judgement, be in need of initial adjunctive therapy after failure to control seizures with AED monotherapy, at the optimal dose and duration. (revised per Amendment 01)
4. Subjects who receive perampanel as monotherapy, who were newly diagnosed (treatment naïve), following the defined diagnosis of epilepsy. (revised per Amendment 01)
5. Subjects who are currently receiving monotherapy treatment may receive perampanel as monotherapy if, in the investigator's judgment, the subject may benefit from a change in monotherapy treatment. Subjects must not have previously received adjunctive AED treatment.
6. If antidepressants or antianxiety drugs are used, subjects must be on a stable dose regimen of these drugs during the 8 weeks before Visit 2 (Week 0).

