#### **9.7.1.6.3 EXPLORATORY EFFICACY ANALYSES**

Analyses of exploratory efficacy endpoints will be performed in the subset of the FAS with sufficient baseline seizure frequency. All summaries will be produced by seizure type (POS, SGS, and PGTCS).

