## 8 DEFINITIONS AND CONVENTIONS FOR DATA HANDLING

### 8.1 EFFICACY DATA HANDLING

#### 8.1.1 Baseline efficacy

All diary data prior to first dose date plus 6-week prior historical data at the time of enrollment will be used in the computation of baseline seizure frequency per 28 days. All subjects should have at least 6 weeks of diary data prior to baseline (Visit 2).

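### Limiting the responder and percent-change analyses to subjects with a baseline seizure can, at low seizure rates, show a reduction with no drug effect

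*SAP*

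**What the plan says.** Protocol 9.7.1.6.3 has the exploratory seizure analyses "performed in the subset of the FAS with sufficient baseline seizure frequency" and gives no number. SAP 5.4.3 supplies it: the "subset of the FAS with sufficient baseline seizure frequency i.e. at least 1 seizure during the baseline". That line is the whole definition of the set used for the 50% and 75% responder rates and for percent change.

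Baseline frequency per 28 days comes from SAP 8.1.1: "All diary data prior to first dose date plus 6-week prior historical data at the time of enrollment". The same section expects at least 6 weeks of data. The protocol collects up to 12 weeks, but subjects may start sooner: "they will not need to complete the full 12 week diary to enter the Titration Period" (Protocol 9.1.1). Protocol 9.1.2 lets Visit 2 coincide with the Screening Visit.

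The lowest qualifying history in Protocol 9.3.1 is "1 unprovoked (or reflex) seizure with EEG evidence of seizures"; the alternative is two seizures more than a day apart. Neither carries a minimum rate or a look-back period. SAP 5.4 notes that there is no control arm and that the analysis is descriptive.

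**The concern.** Membership of the set and the denominator of every percent change are the same random count. Dropping subjects whose baseline happened to contain no seizure leaves a group whose recorded baseline is, on average, higher than its true rate. On treatment the group drifts back toward that rate whatever the drug does.

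The entry rules admit subjects with few seizures, and that is where the drift is largest. These analyses are the only ones planned for the first two exploratory objectives (responder rates and median percent reduction). With no control arm, nothing in the planned tables separates selection from drug effect. Neither document mentions regression to the mean, an expected no-effect responder rate, or an analysis that keeps zero-baseline subjects.

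**Working it through.** The plan states no responder rate, percent change or seizure rate, so there is no figure of its own to reproduce. The check asks what the planned tables would show if the drug did nothing.

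**From the documents:** threshold of at least 1 baseline seizure (SAP 5.4.3); baseline of 6 weeks (minimum, SAP 8.1.1) or 12 weeks (maximum, protocol); Maintenance of 39 weeks; a 3-month time point, taken as 13 weeks.

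**Assumed:** the same true rate before and on treatment; Poisson counts; rates either common to all subjects or gamma-distributed with shape 1; mean of 1, 2 or 6 seizures per 12 weeks (6 per 12 weeks is 2 per 28 days); no dropout.

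**Selection alone.** With a common rate and mean baseline count m, E[B | B>=1] = m / (1 - exp(-m)). The retained group's true rate divided by its recorded baseline is therefore 1 - exp(-m).
- m = 1: 0.632, a 37% fall.
- m = 2: 0.865, a 14% fall.
- m = 0.5 (the m = 1 rate over 6 weeks): 0.393, a 61% fall.

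With gamma rates the falls are 25%, 11% and 44%. These are group ratios that show the mechanism. The SAP plans subject-level statistics, which come next.

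**One responder rate by hand** (common rate, m = 1, 12-week baseline, 13 weeks). On-treatment count M is Poisson with mean 13/12 = 1.083: P(M=0) = 0.339, P(M<=1) = 0.705, P(M<=2) = 0.904. Baseline counts given B>=1: 0.582, 0.291, 0.097 and 0.024 for B = 1 to 4. Most seizures allowed for a 50% response: 0, 1, 1, 2. Sum: 0.582 x 0.339 + 0.291 x 0.705 + 0.097 x 0.705 + 0.024 x 0.904 = 0.493. Counts of 5 or more add about 0.005, giving 50%.

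**Planned statistics with no drug effect** (2 million simulated subjects per row):

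| Mean per 12 wk | Rates | Baseline | Median change, 39 wk | Mean change, 39 wk | 50% resp., 13 wk | 50% resp., 39 wk |
|---|---|---|---|---|---|---|
| 1 | common | 12 wk | -38% | -23% | 50% | 37% |
| 1 | gamma | 12 wk | -38% | -15% | 47% | 37% |
| 2 | common | 12 wk | -8% | +15% | 33% | 19% |
| 2 | gamma | 12 wk | -15% | +3% | 35% | 24% |
| 1 | common | 6 wk | -54% | -56% | 75% | 68% |
| 1 | gamma | 6 wk | -54% | -40% | 63% | 54% |
| 2 | common | 6 wk | -31% | -23% | 50% | 33% |
| 2 | gamma | 6 wk | -31% | -15% | 46% | 36% |
| 6 | common | 12 wk | +3% | +25% | 12% | 5% |
| 6 | gamma | 12 wk | -4% | +14% | 20% | 12% |
| 6 | common | 6 wk | about 0% | +30% | 17% | 10% |
| 6 | gamma | 6 wk | -8% | +10% | 25% | 17% |

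**Count noise.** Not all of this is selection. A subject whose single 12-week baseline seizure is exactly the true rate still has a 34% chance (P(M=0) above) of being a 50% responder at 13 weeks.

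**A higher threshold.** Common rate of 1 per 28 days, 6-week baseline, 39 weeks: with minimums of 1, 2, 3 and 4 seizures the no-effect median change is -15%, -38%, -58% and -65%, and 50% responders are 21%, 36%, 64% and 91%. With gamma rates of the same mean, the median goes from -23% to -33% and responders stay at 27-28%.

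**Keeping everyone.** Total Maintenance rate over total baseline rate in all subjects, zero-baseline included, was within 0.3% of no change in every row.

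**The case against.** Percent change is undefined for a subject with no baseline seizure, so one seizure is the lowest cut the endpoint permits, and the restriction itself comes from the protocol. That stands: the cut at one is not an error to be corrected by moving it, and a higher cut selects as strongly or more.

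The documents give no seizure rates, so the size cannot be fixed, and at higher rates the effect fades. That stands too. A reader might infer that the tables must show a fall and many responders whatever the drug does. The documents do not support this: at about 2 seizures per 28 days the no-effect median is near zero, and the mean percent change, which the SAP also reports, is positive. With a 12-week baseline the mean is already positive at 2 per 12 weeks.

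A reader might also infer that, for subjects with 1 to 3 baseline seizures, a 75% response is the same as seizure freedom, and so split the tables at 4. That equivalence needs a 12-week baseline and a 13-week window. Over 39 weeks with the same baseline, two baseline seizures allow one on treatment (0.25 x 2 x 39/12 = 1.6). With a 6-week baseline and 13 weeks they also allow one (0.25 x 2 x 13/6 = 1.1).

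Finally, the endpoints are exploratory and descriptive, and SAP 7 says enrolment stopped early, with too few subjects for confidence intervals. This argues against a model by seizure type or a new lead result. It does not argue against one simple supplementary table.

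**Conclusion.** The concern holds in a conditional form. Because the baseline count both admits the subject and forms the denominator, the planned responder and percent-change tables can, at low seizure rates, show a reduction and many responders with no drug effect. For a mean of 1 to 2 seizures per 12 weeks, a 12-week baseline and full follow-up, the no-effect median over 39 weeks is about -8% to -38%, with 50% responders of 33-50% at 13 weeks and 19-37% over 39 weeks. The 6-week minimum baseline enlarges this. At about 2 or more per 28 days the median is near zero.

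These sizes rest on assumed rates, Poisson counts and no dropout, and part of the responder rate is count noise from a short baseline. Retention, seizure freedom and conversion to monotherapy do not use this subset and are unaffected. The change is a cheap improvement to the interpretation of exploratory results.

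**What to change.** In SAP 5.4.3, keep the prespecified responder and percent-change tables and add:

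- A supplementary exploratory summary in all FAS subjects, including those with no baseline seizure, by seizure type: total Maintenance seizures per observed day divided by total baseline seizures per observed day, with a subject-level bootstrap interval if numbers allow.
- The distribution of baseline counts and baseline lengths beside the responder tables.
- A sentence stating that regression to the mean from enrolling subjects soon after a seizure remains. The whole-FAS ratio removes the subset selection, not that.

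The cost is SAP wording and one extra table from data already collected. The added figure is likely to look less favourable, and a ratio of totals can be dominated by subjects with frequent seizures. Subjects who leave before Maintenance add baseline days only, so show the number contributing to each total.
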